Izekizumab Administration			X																Subjects will fast (water is permitted) from 1 hour before until 1 hour postdose.
Izekizumab PK Sample			P	X	X	X	X	X	X	X		X		X		X	X		
Immunogenicity Sample			P					X		X							X	A time-matched PK should be taken at each immunogenicity sample time point.	
Pharmacogenetic Sample			P																
AEs and Concomitant Medication	X	X	X	X	X	X	X	X	X	X	X	X	X	X	X	X	X	If an AE of ISR is reported, the investigator or designee will complete a supplemental ISR AE form.	

Abbreviations: AE = adverse event; BMI = body mass index; CRU = clinical research unit; C-SSRS = Columbia Suicide Severity Rating Scale; d = days; ECG = electrocardiogram; ED = early discontinuation; FSH = follicle-stimulating hormone; HADS = Hospital Anxiety Depression Scale; ISR = injection site reaction; P = predose; PK = pharmacokinetics; TB = tuberculosis; TST = tuberculin skin test.

3. Introduction

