10.3.2.2. Pharmacokinetic Statistical Inference

Pharmacokinetic parameters will be evaluated to determine the bioequivalence of ixekizumab alternate formulation (test) compared to the ixekizumab commercial formulation (reference). Log-transformed C_{max} and AUC parameters will be evaluated in a linear mixed-effects model

with fixed effects for formulation and a random effect for subject. The treatment differences will be back-transformed to present the ratios of geometric means and the corresponding 90% CI.

The t_{max} will be analyzed using a Wilcoxon rank sum test. Estimates of the median difference based on the observed medians, 90% CIs and p-values from the Wilcoxon rank sum test will be calculated.

Bioequivalence will be concluded if the 90% CI is completely contained within the interval (0.80, 1.25).

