7. SAMPLE SIZE JUSTIFICATION

Up to approximately 240 subjects may be enrolled so that approximately 216 subjects (108 in the 80-mg ixekizumab commercial formulation [reference] group and 108 in the 80-mg ixekizumab alternate formulation [test] group) complete the study.

A sample size of 108 subjects per treatment group will provide approximately 90% power that the 90% confidence interval (CI) of the geometric mean ratio of maximum observed drug concentration (C_{max}) and area under the concentration versus time curve (AUC) between groups will fall within equivalence range of 0.8 to 1.25. This sample size calculation was based on the assumptions that the PK parameters have log-normal distribution, the percent coefficients of variation (CV%) of C_{max} and AUC are less or equal to 48% (from study RHCT), the expected ratio of geometric means is between 0.997 to 1.04, and the CV% are the same for subjects from each treatment group.

Subjects who are randomized but not administered treatment and subjects who do not complete PK sampling (including Day 85) may be replaced so that approximately 216 subjects (108 for each treatment) complete the study.

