9.3 Pharmacokinetic Assessment

9.3.1 Pharmacokinetic Analysis

Non-compartmental methods applied with a validated software program (Phoenix WinNonlin Version 8.1 or later) to the serum concentrations of ixekizumab will be used to determine the following PK parameters, when possible:

Parameter	Units	Definition
AUC(0-t _{last})	µg.day/mL	area under the concentration versus time curve from time zero to time t, where t is the last time point with a measurable concentration
AUC(0-∞)	µg.day/mL	area under the concentration versus time curve from time zero to infinity
C _{max}	µg/mL	maximum observed drug concentration
t _{max}	day	time of maximum observed drug concentration
t _{last}	day	time of last observed drug concentration
t _{1/2}	h	half-life associated with the terminal rate constant (λ_z) in non-compartmental analysis
CL/F	L/h	apparent total body clearance of drug calculated after extra-vascular administration
V _Z /F	L	apparent volume of distribution during the terminal phase after extra-vascular administration
V _{ss} /F	L	apparent volume of distribution at steady state after extra-vascular administration

Additional PK parameters may be calculated, as appropriate. The software and version used for the final analyses will be specified in the CSR. Any exceptions or special handling of data will be clearly documented within the final study report.

Formatting of tables, figures and abbreviations will follow the Eli Lilly Global PK/PD/TS Tool: NON-COMPARTMENTAL PHARMACOKINETIC STYLE GUIDE. The version of the tool effective at the time of PK analysis will be followed.

General PK Parameter Rules

- Actual sampling times will be used in the final analyses of individual PK parameters, except for non-bolus predose sampling times which will be set to zero.
- C_{max} and t_{max} will be reported from observed values. If C_{max} occurs at more than one time point, t_{max} will be assigned to the first occurrence of C_{max}.
- AUC parameters will be calculated using a combination of the linear and logarithmic trapezoidal methods (linear-log trapezoidal rule). The linear trapezoidal method will be applied up to t_{max} and then the logarithmic trapezoidal method will be used after t_{max}. The minimum requirement for the calculation of AUC will be the inclusion of at least three consecutive serum concentrations above the lower limit of quantification (LLOQ), with at least one of these concentrations following C_{max}.

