9.3.2 Pharmacokinetic Statistical Methodology

PK parameters will be evaluated to determine the bioequivalence of ixekizumab alternate formulation (test) compared to the ixekizumab commercial formulation (reference). Log-transformed C_{\max} , $\text{AUC}(0-\infty)$ and $\text{AUC}(0-t_{\text{last}})$ will be evaluated in a linear mixed-effects model with fixed effects for formulation and a random effect for subject. The treatment differences will be back-transformed to present the ratios of geometric means and the corresponding 90% CI.

Example SAS code:

```
proc mixed data=pk;
  by parameter;
  class formulation subject;
  model log_pk= formulation / residual ddfm=kr;
  random intercept / subject=subject;
  estimate 'Test - Ref' trtmnt -1 1 / cl alpha=0.1;
run;
```

The t_{\max} will be analyzed using a Wilcoxon rank sum test. Estimates of the median difference based on the observed medians, 90% CIs and p-values from the Wilcoxon rank sum test will be calculated.

Bioequivalence will be concluded if the 90% CI is completely contained within the interval (0.80, 1.25).

PK parameters may be normalized by body weight for summarizing the data and may be summarized by site of injection location using descriptive statistics. Additional comparisons may also be conducted as necessary.

A sensitivity analysis will be performed to complete the statistical comparison above using the subjects who completed the PK sampling schedule to Day 85 only (subjects with no missing PK samples).

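### The tmax difference is estimated from the observed medians but its 90% CI comes from the rank sum test, so the estimate can fall outside its own interval.

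*SAP*

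**What the plan says.** SAP 9.3.2 states that tmax "will be analyzed using a Wilcoxon rank sum test" and then lists what will be calculated: "Estimates of the median difference based on the observed medians, 90% CIs and p-values from the Wilcoxon rank sum test". Protocol 10.3.2.2 has the same rule ("Estimates of the median difference based on the observed medians, 90% CIs and p-values"), as does the synopsis. None of the three says how the interval is built, names a shift estimator, or mentions ties. SAP 9.3.2 gives example code for the mixed model but none for tmax.

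Two other rules matter. Under SAP 9.3.1, Cmax and tmax "will be reported from observed values", so tmax can only be a time at which a sample was drawn. The same section says "Actual sampling times will be used in the final analyses of individual PK parameters". In the protocol's Schedule of Activities, the PK samples around the peak fall on Days 3, 5, 8, 11 and 15. The visit windows are ±1 day on Days 5, 8 and 11 and ±2 days on Day 15.

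Protocol 10.3.2.1 makes Cmax and the two AUCs primary. It lists tmax among other parameters that may be reported.

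**The concern.** A 90% interval obtained by inverting the rank sum test covers the location shift. The point estimate that belongs to it is the median of all test-minus-reference pairwise differences. The difference between the two sample medians is another statistic, and nothing ties it to that interval.

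The sampling grid makes the gap visible. With dosing on Day 1, tmax clusters at about 2, 4, 7, 10 and 14 days postdose. If about half of an arm has peaked by one sampling day, moving a few subjects to the next day moves the sample median by 2 to 3 days, while the shift estimate hardly moves. At stake is a results table in which the tmax estimate and its interval contradict each other. A reader could then misjudge how absorption timing compares between the formulations.

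**Working it through.** **The plan's own figure.** The plan states no figure for tmax. Its only stated figure is about 90% power with 108 per arm for Cmax and AUC, and it reproduces. The log-scale SD is √ln(1 + 0.48²) = 0.4553, and SE = 0.4553 × √(2/108) = 0.0620. At a true ratio of 1.04 the two one-sided tests give power of 90.2% (normal approximation) or 90.1% (noncentral t). The arm size of 108 is used below.

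**A worked example.** The counts are constructed, because the documents contain no tmax data.

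| Days postdose | 2 | 4 | 7 | 10 | 14 |
|---|---|---|---|---|---|
| Test (n = 108) | 20 | 33 | 38 | 12 | 5 |
| Reference (n = 108) | 20 | 35 | 36 | 12 | 5 |

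The arms differ by two subjects, at days 4 and 7.

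- *Medians* (mean of the 54th and 55th ordered values). In the test arm 20 + 33 = 53 subjects are at day 4 or earlier, so the median is 7. In the reference arm 20 + 35 = 55 are, so the median is 4. The planned estimate is 7 − 4 = +3 days.
- *Pairwise differences.* There are 108 × 108 = 11,664.
  - Zero: 20×20 + 33×35 + 38×36 + 12×12 + 5×5 = 3,092.
  - Positive: 33×20 + 38×55 + 12×91 + 5×103 = 4,357.
  - Negative: 11,664 − 3,092 − 4,357 = 4,215.
- *Interval.* The large-sample rank is k = ⌊mn/2 − 1.645 × √(mn(m+n+1)/12)⌋ = ⌊5,832 − 1.645 × √210,924⌋ = 5,076. The limits are the 5,076th and 6,589th ordered differences. The zeros occupy positions 4,216 to 7,307, so the 90% CI is [0, 0].
- *Hodges-Lehmann estimate.* The middle differences, the 5,832nd and 5,833rd, are also 0.
- *Test.* The rank sum p-value is 0.87.

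The planned output would read: +3 days, 90% CI 0 to 0, p = 0.87.

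**How often.** I simulated trials with 108 per arm and 1,000 to 1,500 runs per scenario. The tmax probabilities are assumptions. The base case was 0.15/0.35/0.35/0.10/0.05 on days 2/4/7/10/14, with the split between days 4 and 7 then varied. Times were either nominal or spread continuously over the visit windows. The table gives the share of trials in which the difference of medians fell outside the rank sum 90% CI.

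| Where the median lies | Share outside |
|---|---|
| On the boundary (50% of subjects at or below day 4), or a slight shift between arms around it | about 50-60% |
| 45% or 55% at or below the boundary | about 26-30% |
| 40% or 60% at or below the boundary | about 3-5% |
| Well inside one sampling category | 0-0.5% |

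Continuous spread over the windows changes the shares little. With identical arms on the boundary they are about 56% at nominal times and 48-52% with full-window spread. It does shrink the discrepancy: the SD of the difference of medians there is about 2 days at nominal times and about 1 day with full-window spread. The Hodges-Lehmann estimate fell outside its interval in 0% of runs in every scenario.

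**The case against.** The strongest objection is that nothing depends on it. tmax is not in the objectives and endpoints table, has no margin, and plays no part in the sample size. The 0.80 to 1.25 rule concerns a ratio and cannot apply to a difference in days. This stands, and it limits the point to how a supportive result is reported.

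Readers also have some protection. SAP 9.1 includes the median in the summary statistics for continuous data, and a 3-day gap beside p = 0.87 would probably prompt a question. That also stands, but it does not justify planning an estimate and an interval that can contradict each other.

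The sentence could be read as leaving the interval method open, and the table shells are not available. That reading is possible but not the natural one. If another interval is intended, the SAP has to name it, so the sentence needs editing either way.

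One might also expect actual sampling times to remove the problem. They do not: with times continuous over the full windows, the share on the boundary is still about half.

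From the top row of the simulation a reader might infer that a contradictory result is more likely than not in this trial. The documents do not support that. It needs the median to sit almost exactly on a category boundary, and the share drops to about 3-5% once the cumulative probability there moves 10 percentage points from 50%. No tmax distribution is given, so where this trial lies in that range is unknown.

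**Conclusion.** The point holds as a mismatch between estimate and interval in a supportive analysis. The example shows that the planned estimate can lie outside its own 90% CI. Under assumed tmax distributions the frequency runs from 0% to about 60%, and the documents cannot narrow that range. The conclusion rests on reading the 90% CI as the rank sum interval and on tmax clustering at the scheduled sampling days.

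A reader might go further and infer that the bioequivalence conclusion is at risk. It is not. That decision uses only the ratio intervals for Cmax and the AUCs, and neither error rates nor power change. This is a worthwhile correction of low severity.

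**What to change.** In SAP 9.3.2, replace the tmax estimate with the Hodges-Lehmann estimate of the test-minus-reference shift and its matching 90% CI (for example PROC NPAR1WAY with the HL option and alpha=0.1). Keep the rank sum p-value and give the two observed medians as descriptive statistics only. Record the change in SAP Section 11, which now says there are none. SAP Section 3 states that the SAP supersedes the protocol's statistical considerations, so an SAP edit is enough even though protocol 10.3.2.2 and the synopsis carry the same sentence.

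The cost is one sentence, one procedure option and one entry in Section 11. There is a small downside: on a coarse grid with heavy ties the Hodges-Lehmann estimate and its interval can both collapse to 0, as in the example. They are then consistent but say little. A table of tmax by sampling day and formulation should therefore be shown alongside.

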9.4 Safety and Tolerability Assessments

9.4.1 Adverse events

Where changes in severity are recorded in the Case Report Form (CRF), each separate severity of the adverse event (AE) will be reported in the listings, only the most severe will be used in the summary tables. A pre-existing condition is defined as an AE that starts before the subject has provided written informed consent and is ongoing at consent. A non-treatment emergent AE is defined as an AE which starts after informed consent but prior to dosing. A treatment-emergent AE is defined as an AE which occurs postdose or which is present prior to dosing and becomes more severe postdose.

If the investigator determines an injection-site reaction (ISR) is clinically significant or it is an unsolicited reporting, the event will be recorded as an AE and findings of the ISR (including induration, pain, edema, pruritus, and erythema) will be captured on the ISR AE form. Any ISRs that are present (besides induration, pain, edema, pruritus, and erythema) will be recorded as AEs at the discretion of the investigator only.

All AEs will be listed. Treatment-emergent AEs will be summarized by treatment, severity and relationship to the study drug. The frequency (the number of AEs, the number of subjects experiencing an AE and the percentage of subjects experiencing an AE) of treatment-emergent AEs will be summarized by treatment, Medical Dictionary for Regulatory Activities (MedDRA) version 22.0 system organ class and preferred term. The summary and frequency AE tables will be presented for all causalities and those considered related to the study drug by the investigator. Any serious AEs will be listed.

Discontinuations due to AEs will be listed.

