Study RHCS was a 3-period crossover design, hence each subject received three 80 mg injections, each separated by 7 days (1 injection from each of the 2 alternate ixekizumab formulations [test] and 1 injection from the commercial ixekizumab formulation [reference]). Safety data collected during the study, including AEs, clinical laboratory tests, and vital signs, indicated that all 3 treatments administered were consistent with previous studies with ixekizumab in healthy subjects. The percentage of subjects reporting TEAEs (all causalities) was generally similar following administration of each treatment (17.5% to 26.2%). The most commonly reported treatment-related TEAEs (all causalities) were in the General Disorders and Administration Site Conditions system organ class, with ISRs being the most frequently reported TEAE overall (18 events in 13 subjects). Injection site rash, injection site hemorrhage, nasal congestion, productive cough, upper respiratory tract infection, headache, pain in extremity, and breast mass were each also reported by at least 2 subjects. Infections and infestations that were considered to be treatment related were reported by 6 subjects overall. The majority of TEAEs were mild in severity.

In Study RHCT, 99 healthy subjects received a single 80-mg SC ixekizumab injection (33 in each group of either the commercial or 2 test formulations). Safety data collected during the study, including AEs, clinical laboratory tests, and vital signs, indicated that all 3 treatments administered had similar safety profiles. The percentage of subjects reporting treatment-related TEAEs was similar following administration of each treatment (30.3% to 45.5%). The most commonly reported treatment-related TEAEs were in the General Disorders and Administration Site Conditions system organ class, with ISRs being the most frequently reported TEAE overall (5 events in 4 subjects). Injection site erythema, abdominal pain, upper respiratory tract infection, and headache were each also reported by at least 2 subjects. The majority of TEAEs were mild in severity. Antidrug antibody response observed in Study RHCT with healthy subjects was approximately 9.1% to 12.1% with a low incidence of neutralizing antibodies.

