Injection site reactions will be captured on the ISR AE form and the eCRF as an AE. The findings of ISR (including induration, pain, edema, pruritus, and erythema) for a specific injection will be captured as a single AE, even if more than 1 of the findings is positive, and the

severity that is recorded on the ISR AE form will be the highest severity across the findings at each applicable visit.

If injection site pain is reported at any time during the study, the intensity of pain will be quantified using the 100-mm validated visual analog scale (VAS) pain score. The VAS is a well-validated tool (Williamson and Hoggart 2005) to assess injection site pain; it is presented as a 100-mm line anchored by verbal descriptors, usually “no pain” and “worst possible pain.” The subject will be asked to rate any pain at the injection site on a scale of 0 to 100 mm on the line as soon as is practical following reporting of the event.

Injection site assessments should be conducted at the next planned visit following the reporting of an injection-related AE.

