9.4.9 Injection-Site Assessments

Injection sites will be assessed for reactions including bleeding, induration, pain, edema, pruritus, and erythema. Any available injection-site assessment data will be listed.

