9.4.10 Visual analog scale (VAS) pain

Intensity of pain data will be quantified using a 100-mm validated visual analog scale (VAS) for any subject that answers “Yes” to the question “How much pain have you had at the injection site?”. The data will be listed and summarized by treatment and time point.

In addition, the severity of pain will be categorized by VAS pain score as no pain (0), mild pain (> 0 and ≤ 30), moderate pain (> 30 and ≤ 70), and severe pain (> 70). The number and percentage of subjects in each pain severity category will be summarized by treatment and time point. The percentage of subjects in each pain severity category will also be presented in a frequency figure. Figures of the continuous injection-site pain VAS score will also be presented, by treatment and measuring time point.

9.4.11 Columbia-Suicide Severity Rating Scale (C-SSRS), Self-Harm Supplement and Hospital Anxiety Depression Scale (HADS)

Given that few or no suicidal ideation or behaviors are anticipated, a listing of C-SSRS data will be produced by subject and visit. Only subjects that show suicidal ideation/behavior or self-injurious behavior without suicidal intent will be included in the listing (i.e., if a subject’s answers are all ‘no’ for the C-SSRS, then that subject will not be displayed). However, if a subject reported any suicidal ideation/behavior or self-injurious behavior without suicidal intent at any time point then all their ideation and behavior will be included, even if not positive.

HADS item scores will be listed for subjects with HADS depression subscale ≥ 11 at any time.

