11. CHANGES FROM THE PROTOCOL SPECIFIED STATISTICAL ANALYSES

There were no changes from the protocol specified statistical analyses.

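### SAP 9.4.1 and protocol 9.4.5.1 use different rules for when an injection-site reaction counts as an adverse event, and the SAP does not declare the difference

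*SAP*

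**What the plan says.** Protocol 9.4.5.1 sets the recording rule: "Injection site reactions will be captured on the ISR AE form and the eCRF as an AE". It attaches no test of significance and gives no discretion. All findings at one injection form a single event, graded at the worst of them. Protocol 9.2.1.1 names ISRs as adverse events of special interest, and the synopsis gives TEAEs and SAEs as the secondary endpoint.

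SAP 9.4.1 sets another rule: "If the investigator determines an injection-site reaction (ISR) is clinically significant or it is an unsolicited reporting, the event will be recorded as an AE". It continues: "Any ISRs that are present (besides induration, pain, edema, pruritus, and erythema) will be recorded as AEs at the discretion of the investigator only".

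On presentation, SAP 9.4.1 tabulates TEAEs by treatment. SAP 9.4.9 says of injection-site assessments: "Any available injection-site assessment data will be listed". SAP 9.4.10 says of the pain VAS: "The data will be listed and summarized by treatment and time point", and adds severity categories and figures. SAP 11 states: "There were no changes from the protocol specified statistical analyses".

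**The concern.** Two case definitions cannot both govern one TEAE table. Under the protocol, an ISR needs only to be present. Under the SAP, some ISRs become events only if the investigator chooses.

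This matters because ISRs were the most frequently reported TEAE in both earlier formulation studies, RHCS and RHCT (protocol 3.3), and local tolerability is why an alternate formulation was developed (protocol 3.2).

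Discretion also carries more risk here than in a double-blind trial. Protocol 7.3 describes a subject-blind study. Under protocol 7.1.1 unblinded staff handle and give the injections, and sites may set up assessor blinding as they see fit. Nothing requires that the person who decides whether a finding is an event be unaware of the formulation.

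**Working it through.** No stated figure tests this point, so the check is a comparison of the texts, followed by an illustration of scale.

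**Step 1. The two rules side by side.** The five named findings are pain, erythema, induration, pruritus and edema.

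| ISR | Protocol 9.4.5.1 | SAP 9.4.1 |
|---|---|---|
| One of the five, unsolicited | AE | AE |
| One of the five, solicited, clinically significant | AE | AE |
| One of the five, solicited, not clinically significant | AE | Not required to be an AE |
| Any other ISR, such as rash | AE | Investigator's discretion |

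The first SAP sentence gives sufficient conditions and does not say outright that all other ISRs are not events. It has no purpose, though, unless some are left out. The two SAP sentences also overlap: an unsolicited rash is an event under the first and discretionary under the second.

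**Step 2. Where the rules part in practice.** The Schedule of Activities has no row for a routine solicited injection-site check. Protocol 9.4.5.1 places site assessments after an injection-related event has been reported. Most ISRs with one of the five findings would therefore be unsolicited and count under both rules, so the third row should be rare. The fourth row is where the definitions really differ, and it is not empty. For RHCS, protocol 3.3 lists, each in at least 2 subjects: "Injection site rash, injection site hemorrhage, nasal congestion, productive cough, upper respiratory tract infection, headache". Rash is the clear example. Hemorrhage is less clear, because protocol 9.4.5.2 records visible bleeding in the eCRF separately and does not call it an adverse event.

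**Step 3. What happens to an ISR that is not raised to an event.** It enters no by-treatment TEAE table. It may not reach the SAP 9.4.9 listing either, because the Schedule of Activities has the supplemental ISR form completed when an ISR adverse event is reported.

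**Step 4. Scale.** The documents do not give the share of ISRs that the SAP rule would drop. I assume a loss u of 0 to 50%.

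- Input: RHCT, 4 of 99 subjects with an ISR (protocol 3.3). 4/99 = 4.0%.
- Expected per arm of 108: 108 × 4/99 = 4.4 subjects.
- With u = 25%: 4.36 × 0.75 = 3.3. With u = 50%: 4.36 × 0.50 = 2.2.
- Equal loss in both arms: the factor (1 − u) cancels, so the ratio between arms is unchanged and the absolute difference shrinks by (1 − u). With assumed rates of 20% and 10%, a difference of 10.0 points becomes 7.5 or 5.0.
- Loss in one arm only, with equal true rates: the ratio moves from 1 to 0.75 or 0.50 (3.3 or 2.2 subjects against 4.4).

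The 4% is a rough guide. It pools three formulations given by prefilled syringe, whereas this study uses an autoinjector, and RHCT reported injection-site erythema separately from ISRs.

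**The case against.** The best defence is that the protocol and the eCRF, not the SAP, decide what sites record. SAP 3 supersedes the protocol's statistical considerations, and SAP 11 speaks of statistical analyses. If sites followed protocol 9.4.5.1, every ISR was recorded and the SAP paragraph has no effect on the data. That stands: undercounting is possible but not shown. It does not remove the conflict, because the SAP still states a case definition for a table it governs, and that definition differs from the protocol's.

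Several stronger readings might be inferred, and the documents do not support them:

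- *The SAP only lists injection-site data.* Pain VAS is summarized by treatment in SAP 9.4.10, and ISRs recorded as events enter the TEAE tables. Only the SAP 9.4.9 data are list-only.
- *The discretion sentence reaches pain, the reason for the new formulation.* It excepts pain and the other four named findings.
- *The SAP hides individual symptoms behind a composite grade.* One event per injection at the worst severity is the protocol's own rule.
- *Unrecorded bleeding or bruising breaches the protocol's ISR rule.* Bleeding has its own eCRF record under protocol 9.4.5.2.
- *The earlier studies show events being lost.* In RHCS, rash and hemorrhage appear among the reported TEAEs, so they were recorded.

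It is also fair to say that protocol 7.1.1 does contemplate assessor blinding. It is optional, so differential recording by arm is a risk and not a finding.

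**Conclusion.** The conflict holds. Protocol 9.4.5.1 and SAP 9.4.1 define an ISR adverse event differently, and the SAP declares no difference. If the SAP rule is applied, the ISR count by formulation may be incomplete or discretionary, mainly for findings outside the five named.

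The size is unknown. The fall from 4.4 to 3.3 or 2.2 subjects per arm rests on the RHCT rate and an assumed loss of 25% or 50%. Any distortion of the ratio also needs loss that differs by arm, which nothing in the documents demonstrates.

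The consequence is limited to a descriptive secondary endpoint, with no safety inference planned (SAP 9.4.13). A reader should not infer any effect on the bioequivalence conclusion, which rests on Cmax and the AUCs. The point is still worth correcting, because ISRs are an event of special interest and the remedy is small.

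**What to change.** 1. Replace the ISR paragraph of SAP 9.4.1 with the rule in protocol 9.4.5.1: each ISR is an adverse event, one per injection, at the highest severity. If the sponsor prefers another rule, reconcile the two documents and declare the difference in SAP 11.

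2. In SAP 9.4.9, add one descriptive table by formulation, drawn from the ISR AE form and the existing eCRF bleeding field: number and percentage of dosed subjects with any ISR, with each finding, and by worst severity.

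The table does not replace the first change. The ISR form is completed only when an ISR event is reported, so the table cannot recover reactions that were never raised to events.

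The cost is SAP wording and one extra table with small counts, and no new assessment.
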